1. BACKGROUND AND STUDY OBJECTIVES

1.1 BACKGROUND

Non-Hodgkin lymphomas (NHL) are a heterogeneous group of lymphoproliferative tumours with varying behaviour and treatment-response patterns (Armitage 1993).

NHL is the most common hematologic malignancy in adults.

The majority of NHLs (also known as malignant lymphoma) are of B-cell origin and are characterized by the expression of a membrane antigen, CD20, which is important in cell cycle initiation and differentiation (Anderson et al. 1984).

NHL can be divided into aggressive and indolent NHL.

Indolent NHLs are a heterogeneous group of malignant lymphomas and account for about one-third of all NHLs.

Follicular lymphoma (FL) is the second most common lymphoma and is the most common subtype of indolent B-cell lymphomas diagnosed in the United States and Western Europe, accounting for approximately 35% of all NHLs, and 70% of indolent lymphomas (Swerdlow et al. 2008).

The clinical course of indolent NHL is characterized by remission and relapse (Gallagher et al. 1986).

Patients who are diagnosed without symptoms can be observed without treatment for several years. However, treatment is required when the patient presents with symptoms at diagnosis or develops symptoms during observation (Izutsu 2014).

Treatment modalities for FL include chemotherapy, radiotherapy and immunotherapy against CD20, and stem cell transplantation, but a standard treatment approach for FL has not been established.

Currently, the first-line treatment for FL is rituximab in combination with chemotherapy, followed by maintenance therapy with rituximab every two months for two years, as demonstrated by results of the PRIMA study (Salles et al, 2011). This regimen had determined a satisfactory result in most of treated patients, with a 10-year progression free survival of 51%.

Despite these encouraging results, therapy for FL is not curative and presents with a chronic course (i.e. remitting-relapsing), with progressively shorter remissions and with increased risk of developing a transformation of the disease, i.e. the transition from an indolent malignant lymphoma to a more aggressive type of lymphoma. The majority of patients will ultimately die from progressive disease.

Therefore, the introduction of new agents that may potentially alter the natural history of the disease is of great interest.

Obinutuzumab is a recombinant monoclonal humanized and glycoengineered Type II anti-CD20 antibody of the IgG1 isotype. It specifically targets the extracellular loop of the CD20 transmembrane antigen on the surface of non-malignant and malignant pre-B and mature B-lymphocytes.

Obinutuzumab has been evaluated in a wide-ranging program of clinical trials in patients with B-cell malignancies. Efficacy as monotherapy has been reported in patients with relapsed/refractory indolent and aggressive NHL (Salles et al. 2012; Salles et al. 2013) and in chronic lymphocytic leukemia (CLL) of B-cell origin (Cartron et al. 2014). Improved outcomes have also been noted when Obinutuzumab has been added to chemotherapy in patients with B-cell NHL (Radford et al. 2013).

In the phase III study (the GALLIUM trial), in patients with previously untreated indolent NHL, Obinutuzumab-based chemotherapy resulted in a significantly lower risk of progression, relapse, or death and in a superior progression-free-survival (PFS) than rituximab-based chemotherapy (Marcus et al. 2017).

A further analysis (Seymour et al, 2018) of the progression of disease at 2 years (POD24) and its impact on overall survival (OS) has shown that treatment with Obinutuzumab plus chemotherapy was associated with a marked reduction of POD24 compared to rituximab-based chemotherapy.

Overall, Obinutuzumab has an acceptable safety profile as emerged from clinical trials. Infusion-related Reactions (IRRs) were the most common AEs throughout all clinical trials (Edelmann et al. 2016). They comprised of various symptoms such as hypotension or hypertension, tachycardia, dyspnea, pyrexia, chills, nausea, vomiting, diarrhea, flushing and headache coinciding with drug infusion. However, IRRs mainly occurred during the first infusion and almost always resolved with slowing or interrupting the infusion and/or upon steroid administration.

Obinutuzumab has also received the approval from the European Medicines Agency (EMA) for use in combination with chemotherapy, followed by Obinutuzumab maintenance therapy in patients with previously untreated advanced follicular lymphoma.

This observational study has been planned to evaluate the effectiveness of Obinutuzumab in combination with chemotherapy in previously untreated advanced FL patients, in the real world setting in Italy.

The study will allow to collect real-life data in a significant number of Italian patients and thus will allow to verify in routine practice the effectiveness and safety management in 50 reference sites all over the country.

1.2 STUDY OBJECTIVES

This study aims to evaluate the effectiveness and safety of Obinutuzumab in patients with previously untreated advanced follicular lymphoma (FL) treated with Obinutuzumab in routine clinical care.

1.2.1 Effectiveness Objectives

The primary effectiveness objective of this study is as follows:

- 1) To evaluate the effectiveness of Obinutuzumab in combination with chemotherapy in previously untreated advanced follicular lymphoma (FL) patients, in the real world setting as measured by the proportion of patients relapsed within 24 months from start of therapy (POD24).

The secondary effectiveness objectives of this study are as follows:

- 2) To evaluate the progression free survival (PFS) at 2 and 3 years;
- 3) To evaluate the overall and complete response rates at mid and end of induction, and during and after maintenance therapy (including the complete response rate at 30 months [CR30]), as per clinical practice, with and without 18F-fluorodeoxyglucose – positron emission tomography (FDG-PET);
- 4) To describe patient/disease characteristics and the second line regimens prescribed for patients who progressed after first line therapy during the overall study duration and within 24 months from start of therapy (POD24);
- 5) To explore the effectiveness of Obinutuzumab in different patient subgroups, stratified by follicular lymphoma International Prognostic Index (FLIPI) – intermediate and high, ECOG performance status (PS), age at study entry, chemotherapy backbone choice, hepatitis infection (history of past/resolved infection or latent HBV after prophylaxis as per standard treatment guidelines), presence of autoimmune disease, history of renal failure and liver failure.

1.2.2 Safety Objectives

The safety objectives of this study are as follows:

- 1) To evaluate the safety of Obinutuzumab in a real-world setting.

1.2.3 Other/Exploratory Objectives

- 1) To describe the treatment pattern in first and second line of treatment;
- 2) To evaluate methods applied to tumour and response evaluations according to used guidelines and clinical practice;
- 3) To evaluate the FDG-PET response at end of induction and end of maintenance, as per clinical practice;
- 4) To evaluate the Quality of life;
- 5) To evaluate the presence of B symptoms;
- 6) To explore effectiveness of Obinutuzumab in real world setting;
- 7) To explore prescription profile;
- 8) To explore COVID-19 impact on therapy adherence

2. STUDY DESIGN

2.1 DESCRIPTION OF STUDY DESIGN

This is a retrospective and prospective primary data collection and secondary data use, non-interventional, multi-center, national (involving approximately 50 Italian centers) study.

Patients should be included after the start of treatment with Obinutuzumab and chemotherapy, including newly diagnosed FL patients. Patients included should have performed at least 2 cycles of induction treatment with Obinutuzumab and chemotherapy within 1 year from beginning of treatment and will be followed up 3.5 years from the start of treatment.

For each patient, the study will consist of a period of 42 months which can include:

- an induction treatment period (approximately 6 months) in which patients will receive Obinutuzumab and chemotherapy;
- a maintenance treatment period (approximately 24 months) in which patients will receive Obinutuzumab monotherapy;
- a follow-up period of one year, after the last Obinutuzumab administration, or up to 3.5 years after start of the treatment for early discontinued patients.

A schedule of activities is provided in Appendix 1.

2.2 DATA SOURCES

Patients' data will be recorded on eCRFs. Data from patient notes should be entered on the CRF as soon as they become available. Data will be collected from patients' records as kept by their attending physicians during daily clinical practice. Initial treatment/pre-treatment data are collected retrospectively. Data will be collected as availability in source document.

Regarding Patient-reported Outcome (PRO), patients will use an electronic PRO (ePRO) device to capture PRO data at in-person clinic visits. In case patient is not able to complete the electronic questionnaires, e.g. due to technical issues, the PRO data will be completed by patient in paper records and later transferred into the electronic system by site staff. In case any survival follow-up contact is conducted by phone or in case of patient's compromised reading ability (e.g illiterate patients/ vision issues, etc) the PRO data for that visit will be collected in an interview performed by a trained site staff (via telephone or face-to-face, depending on how visit occurs), recorded in paper records (source document) and then transferred in electronic system.

2.3 PRIMARY OUTCOME MEASURES

Progression of disease at 2 years (POD24), defined as the time from the date of treatment initiation with Obinutuzumab until the first documented progression of disease

or death due to disease progression, whichever occurs first, within 24 months from the start of treatment with Obinutuzumab. Patients who have no disease progression and have not died due to disease progression or who are lost to follow-up at the time of analysis will be censored at the date of last tumor assessment where no progression was documented or the last date of follow-up for disease, whichever is last. Patients without post-baseline tumor assessments will be censored at the time of their baseline visit unless death due to disease progression occurs prior to their first scheduled tumor assessment. Patients who die for reasons not related to the disease progression within 24 months from the treatment start with Obinutuzumab will be excluded from the statistical analysis of the endpoint.

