6.4.2 Data Collected during the Observation Period

During therapy with Obinutuzumab, laboratory assessments are routinely performed in accordance with current guidelines and local standard of care. When performed during the observational period, available results that represent an adverse event in accordance to CTCAE vs. 5, relevant symptom/signal of an event or abnormal laboratory finding that results in a change of the treatment in study will be documented in the eCRF. Most data will be documented during the treatment period when the respective assessments are usually performed according to standard of care. The proposed assessments and suggested timings for assessments in the protocol/observational plan are not mandatory. It is up to the treating physician to perform and document the assessments as performed in the real clinical setting.

In the routine care setting, patients are seen regularly by their treating physicians either for treatment or for regular assessment after treatment. Thus, no study-specific visits or evaluations are required by this protocol.

Tumor assessments collected in eCRF will comprise the following periods as available:

- Baseline tumor assessment
- During induction:
 - Mid induction: tumor assessment performed between cycle 2 and cycle 4 after the start of treatments
 - End induction: tumor assessment performed at the day of cycle 6 /8 (or when induction is early discontinued) until 2 month later
- After induction treatment:
 - 1 year after the start of treatment (from 10 to 14 months after the start of treatment)

- 2 years after the start of treatment (from 22 to 26 months after the start of treatment)
- 3 years after the start of treatment (from 34 to 40 months after the start of treatment)
- 1 year after end of maintenance as applicable
- Any tumor assessment, and the method used that shows disease progression, CR or CRu during induction or maintenance.

The lack of tumor assessments in those periods are not a protocol deviation as clinical practice should be followed.

Since the enrolment of patients into the study will occur after the treatment has already started (Patients included should have performed at least 2 cycles of induction treatment with Obinutuzumab but no later than the completion of 1 year of the treatment with Obinutuzumab), a retrospective data collection is expected.

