2.4 SECONDARY OUTCOME MEASURES

2.4.1 Secondary Effectiveness Outcome Measures

- Progression free survival (PFS) at 2 and 3 years, defined as the time from the date of treatment initiation until the first documented progression of disease measured by routine clinical care or death from any cause, whichever occurs first. Patients who have no disease progression and have not died or who are lost to follow-up at the time of analysis will be censored at the date of last tumor assessment where no progression was documented or the last date of follow-up for disease, whichever is last. Patients without post-baseline tumor assessments will be censored at the time of their baseline visit unless death occurs prior to their first scheduled tumor assessment;
- Time to next treatment (TTNT), defined as the Time to initiation of subsequent systemic anti-cancer therapy following initiation of Obinutuzumab containing therapy. Patients not starting a subsequent systemic anti-cancer therapy will be censored at the date of the last study visit;
- Overall survival (OS), defined as the time from initiation of study treatment to death from any cause. Patients who still alive at the time of analysis and patients who are lost to follow-up will be censored at their last time known to be alive;
- Correlation between POD24 and OS;
- TTLCB, defined as the time from first dose to loss of clinical benefit as assessed by the treating physician (single or multiple reasons possible: e.g. disease progression, deterioration in ECOG PS, death, other). Patients who do not loss clinical benefit will be censored at the date of the last study visit. Patients without post-baseline tumor assessments will be censored at the time of their baseline visit unless death occurs prior to their first scheduled tumor assessment;
- Overall response rate (ORR);
- Complete response (CR);
- Complete response at 30 months (CR30);

- Duration of response (DoR) measured per clinical practice, defined as the time from first documentation of CR or partial response (PR) (whichever occurs first) until disease progression, as evaluated by the physician according to routine clinical practice or death. Patients who have no disease progression and have not died or who are lost to follow-up at the time of analysis will be censored at the date of last tumor assessment where no progression was documented or the last date of follow-up for disease, whichever is last;

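### The rule for patients without a post-baseline tumor assessment cancels observed non-fatal TTLCB events and makes POD24 and PFS deaths depend on an undefined first scheduled assessment

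*SAP*

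**What the plan says.** Below, an unassessed patient is one with no tumor assessment after baseline.

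- **POD24** (SAP 2.3; same text in Protocol 6.3.1 and the synopsis). "Patients without post-baseline tumor assessments will be censored at the time of their baseline visit unless death due to disease progression occurs"; the exception in full is "unless death due to disease progression occurs prior to their first scheduled tumor assessment". The sentence just before it censors event-free patients at the last progression-free assessment "or the last date of follow-up for disease, whichever is last".
- **PFS and TTLCB** (SAP 2.4.1; Protocol 6.3.2 and the synopsis). Both carry the sentence "Patients without post-baseline tumor assessments will be censored at the time of their baseline visit unless death occurs prior to their first scheduled tumor assessment". TTLCB itself is the treating physician's judgement, and the reasons listed as examples are "disease progression, deterioration in ECOG PS, death, other".
- **Assessment schedule** (Protocol 6.4.2). "The proposed assessments and suggested timings for assessments in the protocol/observational plan are not mandatory", and "no study-specific visits or evaluations are required by this protocol". On missing assessments: "The lack of tumor assessments in those periods are not a protocol deviation as clinical practice should be followed".
- **Progression without imaging** (Protocol Appendix 3.3.10). In rare cases progression may be determined from worsening symptoms.
- **Safeguards.** SAP 3.4 plans no sensitivity analysis and SAP 3.6 no handling of missing data. OS and TTNT carry no baseline-censoring sentence.

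**The concern.** A censoring rule should say when observation stops for patients who have had no event. This one goes further and takes in patients whose event was observed.

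For TTLCB, a physician can record and date a loss of benefit from declining performance status without any tumor assessment. The rule then returns that patient to baseline as censored. For POD24 and PFS, the rule keeps a qualifying death only if it precedes an assessment whose date the plan never fixes, so two analysts could classify the same death differently. What is at stake is a few events in the primary endpoint and in two secondary ones, with no planned analysis that would show how many.

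**Working it through.** **1. TTLCB, by comparing the sentences.** The definition accepts performance-status decline, or another reason, as an event. The last sentence of the same bullet censors every unassessed patient at baseline, with early death as the only exception. Take a patient with a dated performance-status decline, alive, with no assessment: an event under the definition, censored at time zero under the last sentence. No interpretation of the schedule is needed. The documents give no expected TTLCB rate, so the effect cannot be sized.

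**2. POD24 and PFS, by possible meanings of the exception.**

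- *The mid-induction window is the first scheduled assessment.* It is given in two ways: between cycles 2 and 4 (Protocol 6.4.2), and 10 to 14 weeks (footnote j of Protocol Appendix 2 and SAP Appendix 1). Later qualifying deaths in unassessed patients are then lost. Entry may be up to 1 year after treatment start, so for anyone enrolled after week 14 the exception can never apply.
- *No schedule exists, so any death in an unassessed patient comes before one.* All qualifying deaths are kept.
- *Each physician's own plan is the schedule.* The result varies by patient.

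The text does not choose between these. A symptomatic progression without an assessment is lost under all three, because only death is excepted. An unassessed, event-free patient with clinical disease follow-up also falls under two sentences that give different censoring dates.

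**3. The plan's own precision.** Inputs from SAP 2.6: 300 evaluable patients, expected POD24 13%, so E = 39 events. The exact Clopper-Pearson interval for 39/300 is 9.4% to 17.3%, width 7.9 points, half-width 3.95. This matches the plan. The 3-year PFS figure also reproduces: 240/300 gives 75.0% to 84.4%, width 9.4.

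**4. Size of the effect.** Let m patients be unassessed and k of them have an event that the rule removes. Patients censored at time zero leave the Kaplan-Meier risk set, so, ignoring other censoring, the estimate is about (E − k)/(300 − m), against E/300 if events are counted. The documents give neither m nor k; all the values below are assumed.

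| m | k | POD24 under the rule | Change from 39/300 = 13.0% |
|---|---|---|---|
| 1 | 1 | 38/299 = 12.7% | −0.3 |
| 3 | 0 | 39/297 = 13.1% | +0.1 |
| 6 | 3 | 36/294 = 12.2% | −0.8 |
| 9 | 3 | 36/291 = 12.4% | −0.6 |
| 9 | 9 | 30/291 = 10.3% | −2.7 |
| 15 | 2 | 37/285 = 13.0% | 0.0 |
| 15 | 8 | 31/285 = 10.9% | −2.1 |

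For 3-year PFS failure (60/300 = 20.0%), one lost event gives 59/299 = 19.7%, and nine of nine give 51/291 = 17.5%.

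The rows with m = 3 and m = 15, k = 2 show that the sign depends on the event rate in unassessed patients. At about the average rate the shift is nil; below it, POD24 rises slightly.

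**The case against.** **The sentence is meant only for event-free patients.** It follows the censoring sentence for such patients, and a sensible analyst might apply it that way. But it makes an exception for death, which is itself an event. If it covered only event-free patients, that exception would have nothing to do. As written, it reaches patients with events.

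**Observed deaths are not shown to be lost.** A reader might infer that the plan discards deaths from POD24 and PFS. That holds only if the mid-induction window is taken as the schedule; on another reading all qualifying deaths are kept. This objection stands, and the supportable claim is that the term is undefined. Deaths also remain in OS.

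**Few patients will be affected.** The data-collection tables list tumor assessments in every period, the protocol wants them in follow-up at a minimum, and observation lasts 42 months. Symptom-based progression is described as rare, with objective documentation sought. This stands too.

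**The direction is not established.** It is tempting to say that the patients removed are those who worsen too fast to be assessed, so that results look too good. Nothing in the documents shows this. Missing assessments may equally reflect local practice or loss to follow-up.

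**A larger shift for the same case.** Three lost events might be read as 36/300 = 12.0%. That keeps the censored patients in the denominator as non-events, which SAP 3.2.1 does not say for the binary analysis.

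**Baseline as enrolment.** A reader might take the baseline visit to be enrolment and conclude that unassessed patients gain event-free time. Protocol 6.4.2 places baseline before treatment, and Appendix 2 names the enrolment visit separately, so this is not supported.

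**Conclusion.** The TTLCB defect follows directly from the text: an observed, non-fatal loss of benefit is cancelled for want of a tumor assessment. For POD24 and PFS, the exception rests on a schedule that the study does not have. Qualifying deaths after mid-induction are lost under one reading, and symptomatic progressions without an assessment are lost on any literal reading.

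The effect is probably small. Each lost event costs about 0.3 point of POD24; the assumed case of six unassessed patients with three events costs about 0.8 point, against a planned half-width of 3.95 points. Even the deliberately extreme nine of nine (2.7 points) stays within that half-width. A shift in favour of the drug requires unassessed patients to have more events than the rest, which the documents do not show. This is a minor point, worth correcting because no planned analysis would reveal it.

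**What to change.** - **TTLCB:** delete the tumor-assessment sentence and use the physician-assessed date of loss of benefit. The existing rule of censoring at the last study visit then covers patients without an event.
- **POD24 and PFS:** count every documented progression or qualifying death at its date, with or without a tumor assessment. Delete the condition about the first scheduled assessment. Censor at the first obinutuzumab dose only event-free patients who have neither a post-baseline assessment nor disease follow-up, so that follow-up credited by the general rule is kept.
- **Reporting:** state how many patients have no post-baseline assessment.

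Make the same edits in SAP 2.3 and 2.4.1, Protocol 6.3.1 and 6.3.2, and the synopsis. The cost is wording plus one count in the output; no new assessments or visits are needed.
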